7.6.2.8 Subgenomic SARS-CoV-2 mRNA levels in respiratory samples in SARS-CoV-2-infected individuals

These analyses will be performed by UKK and reported in a separate report which will be appended to the CTR.

7.6.2.9 The pharmacokinetic profile of DZIF-10c, including elimination half-life, peak serum concentration, area under the curve, clearance, and volume of distribution

Same analysis will be performed as described in [Section 7.6.1.9](#).

7.7 EXTENT OF EXPOSURE

Analyses of exposure will be based on the treated set and presented according to trial part and dose cohort. Reason for early stoppage of infusion/inhalation will be presented.

Only descriptive summary statistics are planned for this section of the report.

7.8 SAFETY ANALYSIS

All safety analyses will be performed on the treated set unless specified otherwise.

7.8.1 Adverse Events

Unless otherwise specified, the analyses of adverse events (AEs) will be descriptive in nature. All analyses of AEs will be based on the number of subjects with AEs and NOT on the number of AEs.

For analysis multiple AE occurrence data on the eCRF will be collapsed into an AE provided that all of the following applies:

- All AE attributes are identical (LLT, intensity, action taken, therapy required, seriousness, reason for seriousness, relationship, outcome, AESI and CTCAE grade (based on version 5)).
- The occurrences were time-overlapping or time-adjacent (time-adjacency of 2 occurrences is given if the second occurrence started on the same day or on the day after the end of the first occurrence).

The analysis of AEs will be based on the concept of treatment emergent AEs. That means that all adverse events occurring after drug intake until the end of the residual effect period (+90 days thereafter) (+7 and +28 days as additional analysis) will be assigned to the treatment. In addition, AEs starting from day 9 until day 91 will be tabulated separately. All adverse events occurring before drug intake will be assigned either to 'screening' or 'post-randomisation' (phase IIa part and for listings only). All adverse events occurring after drug intake +90 days will be assigned to 'post-study' (for listings only). For details on the treatment definition, see [Section 6.1](#).

Adverse events related to infusion-related reactions (AEs presenting as hypersensitivity/allergic reaction, anaphylaxis, or cytokine release syndrome) as well as inhalation-related reactions presenting as allergic reaction (e.g., bronchospasm that may manifest with wheezing and/or respiratory distress) will be considered as protocol-specified AESIs, and ticked as such in the eCRF. Further adverse event groupings by safety topic have been defined outside the trial protocol, which will be continuously updated at project level (2). These safety topics are deemed of particular importance, and these definitions can be based on selection of coded terms

based on MedDRA. The latest approved version of the project level overview archived prior to either DBL will be used in the corresponding CTR.

An overall summary of adverse events having occurred during trial participation will be presented, including all AEs occurring:

- Within the first 7 days after drug administration
- Within the first 28 days after drug administration (sensitivity analysis)
- At any time during trial participation after drug administration (sensitivity analysis)

The frequency of subjects with adverse events per cohort and trial part, will be summarised by treatment, primary system organ class and preferred term. Separate tables will be provided for subjects with protocol-specified adverse events of special interest (as ticked in the AE page of the eCRF). Displays will also be provided for subjects with any adverse events, non-serious SAEs, severe adverse events and also serious adverse events, for subjects with adverse events occurring with an incidence in preferred term greater than 5% (in at least one treatment arm), for subjects with adverse events leading to treatment discontinuation, for subjects with investigator defined drug-related adverse events, for subjects with drug-related serious adverse events, and for subjects with adverse events leading to death.

In addition, there will be outputs showing the total number of adverse events, not the number of subjects with adverse events.

Additional outputs will be created for the subgroups depicted in [Section 6.4](#) focusing on the overall summary of adverse events, subjects with serious adverse events and subjects with related adverse events.

The system organ classes will be sorted according to the standard sort order specified by EMA, preferred terms will be sorted by frequency in the DZIF-10c arm (within SOC). In the phase I part, sorting will take place by overall frequency, as every subject receives DZIF-10c. In the phase IIa part of the trial combined safety outputs might be produced if deemed helpful.

7.8.2 Laboratory data

The analyses of laboratory data will be descriptive in nature and based on SI units. All analyses will be performed on the treated set, separately for the different trial parts. Clinically relevant abnormalities will be added as adverse events, but also shown as summary statistics as well as lab shift tables based on CTCAE grades (based on version 5) of standardised values. In addition descriptive visit-by-visit and baseline-last values statistics based on normalised values will be created.

A descriptive evaluation of liver enzymes and bilirubin elevations covering the complete time of trial participation will be given as well. E-dish plots may be created for ALT and AST as well. Please also see [Section 5.4.4](#).

7.8.3 Vital signs

Only descriptive summary statistics will be presented for observed values and change from baseline by treatment and visit. The frequency of subjects with marked changes in vital signs

will also be summarised by treatment according to the parameters defined in [Section 5.4.5](#) of this document.

7.8.4 ECG

Not applicable.

7.8.5 Others

To support the clinical trials disclosure process special safety displays may be necessary, e.g. the number of non-serious adverse events. All required outputs (including the following information) will be included in Appendix 16.1.13.1 of the CTR:

- Number of subjects included by country
- Number of subjects inside (member states) and outside the EU (third countries)
- Frequency of serious drug-related AEs by treatment, primary system organ class and preferred term.

9. ADDITIONAL SECTIONS

9.1 INTERIM ANALYSES

There will be two interim analyses in study Uni Koeln 4370 / BI Trial 1487-0005. The following sections will provide a detailed overview of which analyses of the ones described previously are going to be implemented. Due to the nature of the analyses additional rules, only pertaining to the interim analyses, will also be described. For the purpose of the interim analyses, database snapshots will be performed. These snapshots will follow processes as applicable at the UKK for interim database lock snapshots. Unblinding will also occur based on processes applicable at the UKK.

Evaluations for these interim analyses will be performed on data structures as provided by UKK.

An initial version of the TSAP will be archived before the snapshot for the first interim analysis is performed. The final version of the TSAP will be signed and archived before the snapshot for the second interim analysis is performed.

9.1.1 Interim analysis 1

9.1.1.1 Time point and general content

This interim analysis will commence when the last treated subject in the phase I part of the trial (Cohort 1C or 2C) has been followed up for safety for 7 days after drug intake. The analysis will evaluate data regarding the safety of subjects in the phase I part of the trial, and the main focus of this assessment will be the determination of the treatment dose to be taken forward into subsequent development stages. Only descriptive statistics of viral load will be calculated and no efficacy analyses will be performed. Preliminary PK data may be added if available by the time this interim analysis occurs.

Only a subset of data points is taken into consideration for this analysis.

9.1.1.2 Datapoints to be cleaned

Selected tables, listings and figures (TLFs) will be created and an overview of the specific TLFs will be available in a separate Table of Contents (TOC) document. The database should be as clean as possible before the snapshot is taken, and 7 days will be allocated to cleaning and reconciliation tasks after the last treated subject in the phase I part of the trial has been followed up for safety for 7 days after drug intake. The data generated at the UKK will then be transitioned to BI via SAS transport files for analysis. Despite all reasonable cleaning efforts, it is conceivable that data points might still not be completely clean at the time point the data snapshot is performed as the trial is ongoing. Please note that all data are taken as they are, and no hard coding will be implemented.

The cleaning and reconciliation efforts will particularly focus on, but are not limited to, the following eCRF pages:

- Pages related to AEs

- Pages related to laboratory data
- Pages related to the administration of trial drug
- Pages related to subject disposition
- Pages related to baseline characteristics including concomitant medications
- Data sources related to nasopharyngeal or oropharyngeal viral load data (central testing)
- Data sources related to PK data (central testing)
- Data sources related to ADA data (central testing)

9.1.1.3 Analyses

The following entities will be evaluated at this interim analysis:

- Trial Subjects
 - Disposition of subjects
 - Demographic characteristics
 - Baseline Conditions
 - Concomitant Therapies
 - Exposure to study medication including compliance
- Safety
 - AE overall summary covering AEs with onset during the first 7 days after drug administration
 - Subjects with DLTs within 7 days of trial drug administration
 - Subjects with AEs within 7 days of trial drug administration
 - Subjects with drug-related AEs within 7 days of trial drug administration
 - Subjects with AEs leading to trial drug administration discontinuation
 - Subjects with SAEs within 7 days of trial drug administration
 - Subjects with AESIs within 7 days of trial drug administration
 - Subjects with transitions of CTCAE grades at baseline and worst grade within 7 days of trial drug administration
 - Subjects with clinically relevant lab abnormalities within 7 days of trial drug administration
- Preliminary Efficacy
 - Descriptive summary outputs of absolute viral load (based on nasopharyngeal swabs) in SARS-CoV-2-infected individuals, as well as absolute and relative changes from baseline, for each assessment time point.
- Preliminary PK/ADA (if data allows)

- The same endpoints and assessments as listed in Sections [5.2.2.1](#) and [5.2.2.2](#) will be performed.

The safety outputs will be repeated covering the first 28 days after drug administration as well as the whole trial duration and from day 9 until day 91. Any table created will be accompanied by a corresponding listing.

Please note that all these outputs will also be included in the final CTR.

9.1.2 Interim analysis 2

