6.3 SUBJECT SETS ANALYSED

- Screened set (SCS):
 - This subject set includes all subjects having signed informed consent and would correspond to the intention-to-treat set (ITT) in the phase I part of the trial.
- Randomised set (RS):
 - This subject set includes all randomised subjects in the phase IIa part of the trial, whether treated or not. This would correspond to the intention-to-treat set (ITT) in the phase IIa part of the trial
- Treated set (TS):
 - This subject set includes all subjects who received any amount of study drug.
- Modified Treated set (mTS):
 - This subject set includes all subjects who received any amount of study drug and did not require replacement in the phase I part of the trial. Details about requirement for replacement can be found below.
- Modified Intention-To-Treat set (mITT):
 - This subject set includes all randomised subjects in the phase IIa part of the trial that received any amount of study drug and who have at least a baseline value and a second measurement in the first week (up to 7 days after drug intake) of viral RNA shedding in nasopharyngeal swabs by qRT-PCR.

- PK parameter analysis set (PKS):
 - This subject set includes those subjects in the TS with at least one valid serum concentration of DZIF-10c available

Participants who are withdrawn from the trial after DZIF-10c administration will not be replaced, except for participants during the dose-escalation phase of the trial that are not followed until at least the day 7 visit after drug administration for reasons not related to safety events. Subjects who were replaced will be excluded from the primary analysis of the primary endpoint. Replacement of subjects will be determined on a case-by-case basis; exclusion of these subjects from the primary analysis will be confirmed by the trial team at the report planning meeting prior to database lock.

Please see [Table 6.3: 1](#) for a general overview which patient set will be used for which type of analyses. Additionally, biomarker analyses might be performed on subsets of the mITT set.

Table 6.3: 1 Subject sets used in the different types of analysis

Type of analysis	Subject set					
	SCS	RS	TS	mTS	mITT	PKS
Primary endpoints			X		X ^[1]	
Further endpoints				X		
Safety data, ADA & treatment exposure				X		
Demographic/baseline characteristics				X		
Disposition		X	X			
PK parameters						X
Viral Load				X ^{[1][2]}	X	

^[1] Will be used for the phase I part of the trial.

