7. PLANNED ANALYSIS

Planned analyses can be categorized based on:

- The study period for which they are performed:
 - Phase I dose escalation and phase IIa expansion cohort.
- The study population for which they are performed:
 - Healthy volunteers or SARS-CoV-2-infected individuals.

Unless specified otherwise, analyses for the phase I dose escalation part and the phase IIa expansion cohort part will be identical. The same will hold true for evaluations including healthy volunteers and SARS-CoV-2-infected individuals.

For End-Of-Text tables, the set of summary statistics is: N / Mean / SD / Min / Q1 / Median / Q3 / Max. In descriptive statistics tables, mean, sd and median will be rounded to one additional digit than the raw data. In case extreme data outside of the expected range are observed, other percentiles may be presented additionally in the phase IIa outputs.

Tabulations of frequencies for categorical data will include all categories depicted in the eCRF and will display the number of observations in a category as well as the percentage (%) relative to the respective treatment group (unless otherwise specified, all subjects in the respective subject set whether they have non-missing values or not). Percentages will be rounded to one decimal place. The category missing will be displayed only if there are actually missing values.

All evaluations are exploratory in nature and p-values will be presented where appropriate.

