9.1.2.3 Analyses

The following entities will be evaluated at this interim analysis:

- Trial Subjects
 - Disposition of subjects
 - Demographic characteristics
 - Baseline Conditions
 - Concomitant Therapies
 - Exposure to study medication including compliance
- Safety
 - AE overall summary covering AEs with onset during the first 7 days after drug administration
 - Subjects with DLTs within 7 days of trial drug administration
 - Subjects with AEs within 7 days of trial drug administration
 - Subjects with drug-related AEs within 7 days of trial drug administration
 - Subjects with AEs leading to trial drug administration discontinuation
 - Subjects with SAEs within 7 days of trial drug administration
 - Subjects with AESIs within 7 days of trial drug administration
 - Subjects with transitions of CTCAE grades at baseline and worst grade within 7 days of trial drug administration
 - Subjects with clinically relevant lab abnormalities within 7 days of trial drug administration
- Preliminary Efficacy
 - Descriptive summary outputs of absolute viral load (based on nasopharyngeal swabs) in SARS-CoV-2-infected individuals, as well as absolute and relative changes from baseline, for each assessment time point.
 - Outputs for phase IIa part only:
 - Plots of absolute change from baseline in viral load by treatment arm
 - Time-weighted average change in viral load
 - Mixed effect Model for Repeated Measures (MMRM) of absolute change from baseline in viral load
- Preliminary PK/ADA (by trial part)
 - The same endpoints and assessments as listed in [Sections 5.2.2.1](#) and [5.2.2.2](#) will be performed, if data allows.

The safety outputs will be repeated covering the first 28 days after drug administration as well as the whole trial duration and from day 9 until day 91. Any table created will be accompanied by a corresponding listing.

In addition to these outputs based on the expansion part, a complete re-run of the analyses of the escalation part (and covered during interim analysis 1 already) will be performed.

Please note that all these outputs will also be included in the final CTR.

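### At both interims, the 28-day, day 9–91 and whole-trial AE percentages count participants still inside those windows as event-free, so they are biased down

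*SAP*

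**What the plan says.** Interim 1: "This interim analysis will commence when the last treated subject in the phase I part of the trial (Cohort 1C or 2C) has been" followed for safety for 7 days (SAP 9.1.1.1). Interim 2 starts at the same point for the last randomised Group 2D participant (SAP 9.1.2.1). A further 7 days are set aside for cleaning before each snapshot (SAP 9.1.1.2, 9.1.2.2), and the interim analyses use everything collected up to the snapshot (SAP 5).

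After listing mainly 7-day safety outputs, SAP 9.1.1.3 has them "repeated covering the first 28 days after drug administration as well as the whole trial duration and from day 9 until day 91". SAP 9.1.2.3 does the same: "The safety outputs will be repeated covering the first 28 days after drug administration as well as the whole trial duration", plus days 9 to 91. It also adds "a complete re-run of the analyses of the escalation part".

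On the analysis set: "All safety analyses will be performed on the treated set unless specified otherwise" (SAP 7.8). The treated set has no follow-up requirement: "This subject set includes all subjects who received any amount of study drug" (SAP 6.3). Phase I primary-endpoint evaluations use the modified treated set instead (SAP 7.4), which drops only replaced participants.

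On the denominator: unless otherwise specified, percentages are taken over "all subjects in the respective subject set whether they have non-missing values or not" (SAP 7). SAP 9.1 announces rules specific to the interims but gives none for a window that is still open.

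**The concern.** A participant dosed 10 days before the snapshot cannot yet have an AE on day 20, but stays in the denominator of the 28-day table. The displayed percentage then mixes risk with length of follow-up.

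In phase I, length of follow-up is tied to dose: each group opens only after the previous group's day 7 review, so the highest dose always has the shortest follow-up. If the true risk were the same at every dose, the longer-window tables would show it falling as dose rises. SAP 9.1.1.1 gives interim 1 the main purpose of identifying the dose for later development, so these tables belong to a package read with dose in mind. At interim 2, the absolute longer-window AE rates reported for Group 2D would be too low.

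The SAP handles incomplete data elsewhere. Ongoing AEs are censored at the snapshot in duration analyses (SAP 6.6.1), and the viral clearance rate uses only participants with data (SAP 7.5.2.2.3). AE incidence has no such provision.

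**Working it through.** **The plan's own AE figures.** No longer-window interim rate is calculated in the documents. Protocol 8.2 gives 90% intervals for AE rates of 20%, 25% and 30% with 20 participants. Using p ± 1.645·√(p(1−p)/20) at 25%: √(0.25×0.75/20) = 0.0968, times 1.645 = 0.159, so 9.1% to 40.9%. The other two give 5.3–34.7% and 13.1–46.9%. All match the printed intervals after rounding. I take 25% as an assumed true 28-day risk; Protocol 8.2 does not tie its rates to a time window.

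**Step 1: fastest escalation calendar.** Inputs from Protocol 4.1.1: 3 participants per group, one per dose per day, next group only after the whole prior group's day 7 visit. Assumption: no delay for SMC review. The last 2C dose falls on day 29, so the trigger is day 29 + 7 = 36 and the snapshot, after cleaning, day 43.

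**Step 2: share of each window observed.** With f = days from dosing to the cut, I averaged min(f, 28)/28 for the 28-day window and min(max(f − 7, 0), 83)/83 for days 9–91 (dosing is day 1 in the SAP, so the window has 83 days). Example, 2C at the trigger: mean f = 8, so 8/28 = 29% and 1/83 = 1%. At the snapshot: 15/28 = 54% and 8/83 = 10%.

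| Groups | Dosing days | f at trigger | 28-day observed: trigger / snapshot | Days 9–91 observed: trigger / snapshot |
|---|---|---|---|---|
| 1A | 0–2 | 34–36 | 100% / 100% | 34% / 42% |
| 1B, 2A | 9–11 | 25–27 | 93% / 100% | 23% / 31% |
| 1C, 2B | 18–20 | 16–18 | 61% / 86% | 12% / 20% |
| 2C | 27–29 | 7–9 | 29% / 54% | 1% / 10% |

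**Step 3: what a true 25% would look like.** Under constant hazard the expected displayed value is 1 − 0.75^(f/28), with f capped at 28. The alternative puts 70% of the 28-day cumulative hazard in the first 7 days. Example, 2C at the trigger with f = 8: 1 − 0.75^(8/28) = 7.9%.

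| Groups | Trigger: constant / front-loaded | Snapshot: constant / front-loaded |
|---|---|---|
| 1A | 25.0% / 25.0% | 25.0% / 25.0% |
| 1B, 2A | 23.4% / 24.4% | 25.0% / 25.0% |
| 1C, 2B | 16.0% / 21.5% | 21.9% / 23.8% |
| 2C | 7.9% / 18.6% | 14.3% / 20.9% |

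**Step 4: slower escalation.** With 7 days of SMC review at each of the three gates, the snapshot falls on day 43 + 21 = 64. Every group except 2C then has at least 28 days. 2C is unchanged at 14–16 days, since its follow-up depends only on the pace of dosing within 2C. No group has completed day 91 (1A has 62–64 days).

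**Step 5: interim 2, Group 2D.** Accrual speed is not given. Assuming 60 participants enrolled evenly over 4, 8 or 12 weeks:

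| | 4 weeks | 8 weeks | 12 weeks |
|---|---|---|---|
| With ≥28 days: trigger / snapshot | 15 / 30 of 60 | 37 / 45 | 45 / 50 |
| Days 9–91 observed: trigger / snapshot | 17% / 25% | 34% / 42% | 51% / 59% |
| True 25% at trigger: constant / front-loaded | 18.4% / 22.5% | 21.6% / 23.7% | 22.7% / 24.1% |
| True 25% at snapshot: constant / front-loaded | 22.1% / 23.9% | 23.5% / 24.4% | 24.0% / 24.6% |

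Allocation is concurrent and 1:1:1 (Protocol 5.9.4), so the expected difference in mean follow-up between arms is zero (chance SD about 5 days with 8-week accrual). If true risks were 20% and 30%, 8-week accrual at the trigger would show 17.3% and 26.0% under constant hazard. The ratio is kept (26.0/17.3 = 1.50), and the difference shrinks from 10 to 8.7 points.

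**Step 6: escalation re-run at interim 2.** If Group 2D opens on day 36 and accrues over 28 days, the trigger is day 36 + 28 + 7 = 71, and 2C has 42–44 days. Its 28-day window is then complete, but days 9–91 are (43 − 7)/83 = 43% observed.

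**The case against.** The strongest case against is that nothing important depends on these percentages.

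- Escalation and the opening of Group 2D rest on the 3+3 rule and SMC review after the day 7 visit (Protocol 4.1.1). Related grade 3 or higher events arising later go to the SMC as events, not percentages (Protocol 3.4). The primary endpoint and the DLT proportion use 7 days (SAP 7.4.1), a window complete at the trigger. This stands. A reader might infer that dose escalation is compromised; the documents do not support that.
- Groups hold 3 to 6 people. With 3 in 2C and a true 25%, the expected shortfall is 3 × (25 − 7.9)/100 = 0.5 participants at worst and 3 × (25 − 20.9)/100 = 0.1 at best. This stands: no rate from 3 people establishes a dose pattern, corrected or not.
- A reader might infer a dose-related distortion at both interims, Group 2D included. It does not hold for Group 2D, whose arms are randomised concurrently.
- Seven days is the trigger, not the data cut. After cleaning, the last participant has about 14 days, so the snapshot columns are the fairer guide.
- The fastest calendar is probably too fast. The tentative plan puts the first visit in Q4 2020 (Protocol 4.1), and SAP version 1.0, dated 25 February 2021, precedes the first snapshot (SAP 9.1, 10). That gives at least 56 days from first visit, or 49 from first dose after a 7-day screening window, against 43 assumed here. Early events also reduce the bias, and Protocol 5.5 expects administration reactions typically within the first hour.
- The denominator is the SAP's general default and is not restated for these tables; the separate list of interim outputs is not available. But nothing in the SAP overrides the default, and the modified treated set does not remove participants with open windows.
- Listings accompany every table, ongoing participants are counted in the disposition table (SAP 7.1), and SAP 7.8.1 labels the 28-day and whole-trial summaries as sensitivity analyses. These help a careful reader but do not correct the percentages.

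**Conclusion.** The point holds and is minor. Followed as written, the plan yields cumulative AE percentages at both interims that are biased down for the 28-day, day 9–91 and whole-trial windows.

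In the escalation cohorts at interim 1 the shortfall grows with dose within each infection stratum and is largest in 2C. With a true 28-day risk of 25%, 2C would show 14.3–20.9% at the snapshot (7.9–18.6% if cut at the trigger) while 1A shows 25.0%. In Group 2D, a true 25% would show as 22.1–24.6% at the snapshot (18.4–24.1% at the trigger), with no systematic contrast between arms.

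These sizes rest on assumed accrual, escalation pace and AE timing, none of which the documents give. Slower escalation shrinks the 28-day bias in the earlier groups, and slower dosing within 2C would shrink it there. The longer windows remain open in every interim 1 scenario computed. The 7-day primary and DLT outputs, the SMC escalation decisions and the final report, where no participant is still ongoing, are unaffected.

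**What to change.** In SAP 9.1.1.3 and 9.1.2.3, including the escalation re-run at interim 2, leave the 7-day tables as they are. For the 28-day, day 9–91 and whole-trial outputs:

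- print, per group or arm, the number who had completed the window by the snapshot;
- report events per participant-day observed within the window, or, where numbers allow, a Kaplan-Meier estimate or a percentage restricted, in numerator and denominator, to those who completed it;
- mark the cumulative rate as not estimable where nobody has completed the window, as for the 28-day rate in 2C at interim 1 in every scenario above.

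The cost is a few lines of SAP text, one derived follow-up variable and a little programming. Interim late-window figures will rest on fewer participants. A rate per participant-day also presumes a roughly constant hazard within the window: if events cluster early, it runs high in the shortest-followed group, so the observed days should be printed beside it. No new data are needed.
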